2.0 Background and Rationale

For over 100 years, surgical removal of the appendix to treat acute appendicitis has been one of the most commonly performed procedures, resulting in nearly \$2 billion in healthcare costs annually. Patients undergoing appendectomy miss a median of 10-14 days from work and only resume "normal" levels of activity 7-21 days after surgery. As an alternative to surgery, the successful use of antibiotics-alone as a treatment for acute uncomplicated appendicitis (AUA) was first reported in 1959 in a large British case series. As surgical procedures and anesthesia became safer, the antibiotics-only approach to appendicitis was usually restricted to patients with more complicated disease, usually followed by an interval appendectomy. The exception was patients who did not have access to prompt surgical services such as Naval submariners whose initial results were very satisfactory. As

Inspired by the antibiotics-only approach results between 1956 and 2015, and with advances in radiologic imaging to diagnose and stage the progression of disease, there were six randomized trials comparing antibiotics to appendectomy among patients with AUA. These trials, all performed in Europe. 6-11 found that nearly 3 out of 4 patients in the antibiotics treatment group avoided surgery in the first year after diagnosis. A meta-analysis of five of these studies (the most recent published in 2015) found that antibiotic treatment was associated with a 46% reduction in complications and less pain and disability than routine appendectomy. 12 No participant deaths occurred in the trials, and the rates of perforation were lower among those in the antibiotic treatment group. However, existing trials suffer from important limitations. These include small sample sizes leading to indeterminate results, lack of imaging leading to potential inclusion of patients with complicated appendicitis and potentially without appendicitis at all, inexact and treatment dependent outcome definitions (rate of appendectomy) and operation/reoperation criteria, arbitrarily prolonged hospitalization, limited use of laparoscopic techniques. inadequate antibiotic regimen activity, and short-term follow-up (no studies followed patients beyond one year). Furthermore, none of these trials included keeping a record of the patient's experience with treatment in a standardized fashion. Perhaps as a result of these evidence gaps, nearly all United States (U.S.) patients with appendicitis (97.5% according to a recent California [CA]-based administrative database analysis¹³ and similar findings in Washington [WA] [personal communication [name]]) undergo appendectomy. Conversely, in Europe where the trials originated, it now appears that 1 in 5 patients with AUA are being offered the antibiotics approach.

It remains to be determined whether patient experience with the antibiotics strategy (performing appendectomy only when the patient gets worse on antibiotics or has a recurrence of disease) is "just as good as" appendectomy. This comparison should consider the overall impact of the treatment on their health, well-being, quality of life (QoL), healthcare burden, and all clinical endpoints (e.g., resolution of symptoms, need for eventual appendectomy, complications). It also remains to be determined what patient and clinical factors are associated with worse outcomes.

2.1 Rationale

The Comparison of Outcomes of Antibiotic Drugs and Appendectomy (CODA) trial aims to test if, from a patient's perspective, the antibiotics strategy is "just as good as" surgery. We believe that patients, clinicians, and the people who pay for healthcare (both patients and insurers) will find the antibiotics approach acceptable if 1) it results in high rates of treatment success, 2) does not increase complications or adverse events (AEs), and 3) provides an equivalent or better patient experience. A large-scale non-inferiority trial is expected to result in a change in

[name] Study Protocol Version 6.1 February 2019

the management of one of the most common human illnesses. If non-inferiority is demonstrated (or superiority of the antibiotics approach identified), that finding will improve patient choice and should support a shift to the less invasive approach. If non-inferiority is not established, results may help to delineate the trade-offs between the two treatment approaches and inform decision-making.

The observation that patients with AUA can be cured with antibiotics-alone has a scientific rationale. Traditionally, appendicitis was thought to result from a blockage of the appendix and that, if left untreated, inevitably led to a perforation. Contrary to this physiologic model, Carr demonstrated that obstruction of the appendix is an unlikely primary cause in the majority of patients and that most are caused by an enteric infection. ¹⁴ A recent randomized trial found an increased rate of appendectomy with early use of computed tomography (CT) imaging and diagnostic laparoscopy, but case reports of appendicitis remission documented by serial CT all suggest that leaving the appendix in place does not inexorably lead to clinical compromise. 15 A concern of clinicians when considering treating AUA with antibiotics is that not removing the appendix may put patients at risk for a more complicated operation and higher morbidity. Evidence suggests, however, that perforated appendicitis is a pre-hospital and pre-antibiotic event and that non-perforated appendicitis is a "different" disease. This theory is supported by a general lack of relation between a delay in surgery of up to 24-36 hours among patients with appendicitis who are treated with antibiotics and perforation rates. 16,17 Most recently, Fusobacterium sp., a genus of enteric Gram-negative anaerobic bacteria, rather than an obstructive stone, was found to be correlated with the presence of appendicitis and the degree of inflammation. 18 What remains to be determined is whether certain bacterial colonies or features of individual immune response are most associated with progression of appendicitis and whether successful outcomes for people undergoing antibiotic management can be predicted based on the patient's characteristics.

An additional rationale for this study is to address limitations of prior trials. To avoid misclassification problems of other trials and consistent with U.S. norms,, all patients will undergo standard radiographic imaging including CT, ultrasound (US), or magnetic resonance imaging (MRI). Patients with an appendicolith will be included in the trial but considered a unique subgroup and will be evaluated as part of a pre-specified analysis (potentially excluding them from future recruitment if an early analysis demonstrates futility related to the primary antibiotic approach not being successful). To reflect usual and emerging techniques in treatment, the study includes both types of appendectomy (open and laparoscopic) and a broad range of antibiotic strategies including the option for an "all outpatient" treatment schedule with once daily dosing of longer-acting agents. Patients in the antibiotics arm will be given a minimum of 24 hours of intravenous (IV) antibiotics (using any appropriate dosing schedule and based on the patient's ability to tolerate oral medication), followed by oral antibiotics for a total of 10 days of antibiotic treatment). Discharge from the hospital or emergency department (ED) or a change in treatment arm will be guided by clinical targets and reasons for change in treatment arms will be assessed. Participants will be followed for up to two years to assess for longer-term complications, eventual appendectomy (performed anywhere), QoL, gastrointestinal symptoms, and decisional regret. To quantify selection bias and to promote generalizability, all patients approached for the study and those who refuse randomization will be characterized at baseline. A parallel cohort of patients who refuse randomization (up to 250 who initiate the antibiotics strategy and 250 who select to undergo the appendectomy strategy) will be surveyed for up to two years. Participants in all cohorts will be given the option to participate in an extended followup that will assess long term complications, eventual appendectomy, QoL, and gastrointestinal symptoms.

3.0 Study Aims and Methods

3.1 Study Aims

Aim 1. Compare patient reported outcomes (PROs) in patients randomized to the antibiotics or appendectomy strategy.

Sub Aim 1. Compare PROs in patients without appendicolith randomized to the antibiotics or appendectomy strategy.

Exploratory Aim A. Assess the rate of eventual appendectomy after starting the antibiotics treatment regimens in the first week, early (1-4 weeks) and late (2-24 months) periods and identify patient clinical characteristics (e.g., appendicolith) as well as clinician and practice site characteristics associated with eventual appendectomy in the antibiotic therapy group.

Aim 2. Compare clinical outcomes in patients randomized to antibiotics versus appendectomy.

Sub Aim 2. Compare clinical outcomes in patients without appendicolith randomized to the antibiotics or appendectomy strategy.

Exploratory Aim B. Compare randomized patients to those in a concurrent observational cohort to identify selection characteristics and outcome differences between the two groups.

The central hypotheses of the CODA trial is that PROs among patients in the antibiotics arm will not be inferior to those in the appendectomy arm and that adverse clinical outcomes will not be significantly worse (non-inferior) among patients being treated with antibiotics.

3.2 Methods

This will be a multi-site, open trial in which participants with AUA are randomized to one of two initial treatment strategies, appendectomy or antibiotics (with appendectomy only for those with a deteriorating clinical condition while being treated with antibiotics or disease recurrence).

The University of Washington's (UW) Surgical Outcomes Research Center (SORCE) will lead a Clinical Coordinating Center (CCC) and Stakeholder Coordinating Center (SCC). The UW Center for Biomedical Statistics (CBS) will serve as the Data Coordinating Center (DCC).

The CCC will coordinate all aspects of the trial. Investigators at SORCE will coordinate the study at the University of Washington Medical Center (UWMC) and up to twenty other clinical sites. Investigators at Olive View-UCLA Medical Center in CA will coordinate the study there and up to four other clinical sites. In preparing for the study, 18 potential hospital sites were engaged and up to 20 will be considered for involvement in the study, based on readiness of infrastructure, staff engagement, patient population characteristics, and number of appendicitis cases.

Prior to study initiation and enrollment, all clinicians and staff who encounter patients with possible appendicitis will complete study-specific training including demonstrating successful use of the antibiotics strategy in five patients and site experience recorded in a non-protected health information (PHI) based registry (www.certain.org/appysurvey) or log reviewed with the study leadership team. All staff engaging patients with appendicitis at all study sites will undergo online and in-person educational and orientation sessions for the topic and the study protocol.

Table 1. Potential Study Sites, Characteristics, and Projected Yearly Volume of Appendicitis.

	Total				N (%)			
Medical Center	n/yr	Female	> 65 Years	Medicaid	Hispanic	Black	Asian	AI/AN*	Pacific Islander
Harborview	47	13 (27.7)	2 (4.3)	12 (25.5)	12 (25.5)	7 (14.9)	7 (14.9)	2 (4.3)	4 (8.5)
Madigan Army	107	33 (53.6)	16 (15.0)	0 (0.0)	4 (3.7)	4 (3.7)	2 (1.9)	0 (0.0)	1 (0.9)
Northwest	77	36 (46.8)	14 (18.2)	8 (10.4)	2 (2.6)	6 (7.8)	6 (7.8)	0 (0.0)	0 (0.0)
Providence	294	147 (50.0)	54 (18.4)	47 (16.0)	26 (8.8)	6 (2.0)	16 (5.4)	5 (1.7)	3 (1.0)
Sacred Heart	180	91 (50.6)	35 (19.4)	18 (10.0)	2 (1.1)	4 (2.2)	2 (1.1)	4 (2.2)	1 (0.6)
Skagit Valley	93	57 (61.3)	21 (22.6)	17 (18.3)	20 (21.5)	3 (3.2)	1 (1.1)	2 (2.2)	0 (0.0)
Swedish	386	179 (46.4)	67 (17.4)	20 (5.2)	35 (9.1)	11 (2.9)	39 (10.1)	0 (0.0)	3 (0.8)
University of Washington	85	38 (44.7)	14 (16.5)	12 (14.5)	8 (9.4)	1 (1.2)	10 (11.8)	2 (2.4)	0 (0.0)
Virginia Mason	87	41 (47.1)	26 (29.9)	2 (2.3)	4 (4.6)	3 (3.5)	8 (9.2)	1 (1.2)	2 (2.3)
Olive View-UCLA	221	85 (38.5)	2 (0.9)	173 (78.3)	183 (82.8)	2 (0.9)	6 (2.7)	0 (0.0)	4 (1.8)
Harbor-UCLA	263	112 (42.6)	4 (1.5)	116 (44.1)	229 (87.1)	19 (7.2)	8 (3.0)	0 (0.0)	0 (0.0)
Los Angeles County+USC	360	148 (41.1)	23 (6.4)	133 (36.9)	236 (65.6)	54 (15.0)	21 (5.8)	1 (0.3)	1 (0.3)
All Sites	2200	980 (44.5)	278 (12.6)	558 (25.4)	761 (34.6)	120 (5.5)	126 (5.7)	17 (0.8)	19 (0.9)

4.0 Participant Screening and Enrollment

4.1 Participant Screening

Patients presenting to the ED will be screened by study investigators and/or study coordinators seven days a week based on alerts from clinicians, staff, or screening of ED logs. Patients will be identified as potential candidates for the study based on inclusion and exclusion criteria collected as part of standard care, including confirmatory diagnostic imaging (CT, US, and/or MRI).

The CODA Screening Form must be completed for all patients ≥18 years of age presenting to the ED (hospital/clinic) with presumptive diagnosis of appendicitis that has not been previously treated. Completion and data-entry of this form is required regardless of patient eligibility to ensure a complete description of the population of interest. Those who do not meet eligibility criteria or have exclusion criteria present will be considered ineligible. Additionally, this form must be completed and entered for patients that were not approached.

Sites are responsible for maintaining their own screening log in accordance with their institutional policies and guidelines. This log should document adequate information such that the research team may disclose to the institutional compliance department that a patient's electronic medical record (EMR) was accessed to screen for potential eligibility for the CODA trial. UW Medicine requires disclosure of accessing the EMR for purposes other than treatment, payment, and health care operations.

Sites are required to provide a monthly de-identified appendicitis census to the UW CCC. This census will be compared to the number of participants reported as screened at each site and will serve as a measure of protocol compliance.

4.1.1 Retrospective EMR review

For patients excluded due to concern for appendiceal cancer or mass, an EMR review that is separate from the scheduled CODA participants EMR review will be completed. This EMR review may be done retrospectively and must be done in accordance with site Institutional Review Board (IRB) recommendations and approvals. The intention of this EMR review is to

fully characterize this particular patient population and to better understand whether or not the CT reading appropriately excludes patients.

EMR review for these patients will include review and abstraction of the following patient records: final pathology report, operative report, radiology images and reports that indicate association with cancer.

EMR review will be completed for patients excluded for the following reasons: 1) appendiceal soft-tissue mass, 2) imaging features of mucocele or tumor, 3) concern for any carcinomatosis on imaging, or 4) qualitative reason indicative of concern for cancer or mass.

Sites will be provided with a list of screening IDs for patients who were ineligible due to the aforementioned reasons.

4.2 Inclusion Criteria

- 1. Adult ≥18 years;
- First clinical diagnosis of AUA established by clinical care team, supported by any of the following usual care radiological tests (CT, US, and/or MRI). AUA is defined by the usual signs, symptoms, and imaging finding of appendicitis without:
 - a. Diffuse peritonitis on clinical exam (i.e., rigid abdomen / four quadrant peritonitis);
 - b. Radiologic findings of:
 - i. Free air;
 - ii. Walled off fluid collection concerning for an abscess;
 - iii. Significant amounts of intra-abdominal fluid throughout abdomen (i.e., more than trace fluid); or
 - iv. Extent of inflammation or adjacent organ involvement on radiologic imaging such that urgent appendectomy is relatively contraindicated or not intended.
- 3. Ability to provide written informed consent in English or Spanish.

4.3 Exclusion Criteria

Participants must not have any of the following exclusion criteria:

- 1. Unable or unwilling to return or be contacted for and/or research surveys;
- 2. Currently incarcerated in a detention facility or in police custody (patients wearing a monitoring device can be enrolled) at baseline/screening;
- 3. Evidence of severe sepsis or septic shock (e.g., new presumed sepsis-related organ dysfunction, elevated lactate, and/or fluid unresponsive hypotension); these patients can be enrolled if signs of sepsis resolve with fluid resuscitation and pain medication administration while in the ED;
- 4. Immunodeficiency (e.g., absolute neutrophil count <500/mm³, chronic immunosuppressive drugs (e.g., oral corticosteroids, anti-TNF agents), or known AIDS [i.e., recent CD4 count <200] assessed by patient history);
- 5. Uncompensated liver failure;

- 6. Taking medication to treat active inflammatory bowel disease (e.g., Crohn's, ulcerative colitis);
- 7. Active treatment for malignancy, not in remission (patients undergoing active chemotherapy or with plans for chemotherapy in the following 30 days are excluded);
- 8. Pregnant or expectation of becoming pregnant in the 30 days following baseline/screening;
- 9. Expected concurrent hemodialysis, peritoneal dialysis, or treatments using indwelling venous catheters or at risk for bacterial seeding of implants;
- 10. Recent (within 90 days) placement of surgical implant (e.g., pacemaker, joint prosthesis, mechanical valve);
- 11. Indwelling Left Ventricular Assist Device (LVAD);
- 12. Patients with another infection (e.g., pneumonia, urinary tract infection) that requires treatment with another antibiotic at baseline/screening;
- 13. Concurrent illness that would otherwise mandate hospitalization outside of appendicitis and associated symptoms at baseline/screening;
- 14. Imaging findings of any of the following that would make the patient ineligible for one arm of the trial:
 - a. Appendiceal soft-tissue mass;
 - b. Imaging features of mucocele or tumor concerning for malignancy of the appendix or in other organs; or
 - c. Concern for any carcinomatosis on imaging;
- 15. Severe allergy or reaction (e.g., immediate urticaria or anaphylaxis) to all of the proposed antibiotics (See Section 4.5);
- 16. Prior enrollment in the study or other investigational drug or vaccine while on study treatment;
- 17. Abdominal/pelvic surgery in the past month; or
- 18. More than seven hours have transpired since the patient received the first parenteral dose of antibiotics.

4.4 Consent Process

The research coordinator and a representative from the medical team will confirm the patient's eligibility for the study based on inclusion and exclusion criteria. A research team member will approach all eligible patients and ask them to review an informed decision making video using a handheld device. The English or Spanish-language video explains both treatment options and the research study using linguistically and culturally appropriate language. In the event that the tablet is malfunctioning or the patient declines to watch the video, the research coordinator will provide an informational pamphlet that includes the same content as the video. There are two versions of the video and pamphlet, one focused on positive messaging, the other negative. Participants who present on odd calendar days will be shown Version 1; those who present on even days will be shown Version 2. Which version was shown to the patient will be documented on the screening form in order to determine whether phrasing outcomes in different ways impacts subject participation. The video and informational pamphlet both conclude with a

request of the patient to read and sign an informed consent document for participation in the randomization cohort.

- For patients consenting to randomization, they will be randomly assigned to either the antibiotics or appendectomy arm immediately following consent and assigned a study ID;
- b. Patients refusing consent to randomization may first be invited to participate in the observational cohort, and if that is declined, may then be offered participation in the EMR review cohort. This will be done by separate consent(s) with the participant selecting one of two participation options:
 - Option 1. Observational cohort (no randomization). Participants selecting the observational cohort will be asked to complete the same research assessment activities as the randomized cohort and will have their appendicitis treated following the same treatment protocols.
 - Option 2. EMR review cohort. Participants selecting this option will be followed by passive EMR review only. They will not be contacted again for study purposes and will not be asked to complete the Baseline Assessment or the Follow-Up Assessments described in Section 5.2.

In summary, depending on the site, there will be two or three consents for this study with the option to participate in the following groups: 1) randomization cohort, 2) observational cohort, and 3) EMR review cohort. Participants may only consent to one study group. The randomization consent will be presented to the patient following the informed decision-making video or material presentation. Patients declining randomization will then be presented with a different consent form to consider participation in the observational and EMR review only cohorts.

Consenting participants will also need to complete a Health Insurance Portability and Accountability Act (HIPAA) form in accordance with their institutional guidelines. For some partnering sites, HIPAA language will be incorporated into the informed consent document but for others, this will be a separate document. For example, the UW requires that a participant sign a separate HIPAA document to indicate consent that their EMR is accessed and reviewed for research purposes. The HIPAA form is not reviewed by the UW's Human Subjects Division but is required per UW Medicine policy.

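### Consent-message version is set by odd or even day of presentation, so participation compared by version shown among approached patients could reflect selective approach and not framing

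*Protocol*

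**What the plan says.** Protocol Section 4.4 (Consent Process) describes the material: "There are two versions of the video and pamphlet, one focused on positive messaging, the other negative". It allocates by date: "Participants who present on odd calendar days will be shown Version 1; those who present on even days will be shown Version 2". The version shown goes on the screening form "in order to determine whether phrasing outcomes in different ways impacts subject participation", so this is a stated research comparison and not only an operational habit.

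The same section sets out who does what. On eligibility: "The research coordinator and a representative from the medical team will confirm the patient's eligibility for the study based on inclusion and exclusion criteria". On approach: "A research team member will approach all eligible patients and ask them to review an informed decision making video using a handheld device". If the tablet fails or the patient declines the video, "the research coordinator will provide an informational pamphlet that includes the same content as the video".

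Section 4.1 (Participant Screening) requires a screening form whether or not the patient is eligible, and adds that "this form must be completed and entered for patients that were not approached". It also compares a monthly appendicitis census with the number screened at each site. Section 11.3 lists consent without either video or pamphlet as an anticipated deviation.

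Neither document describes a random sequence for the version, concealment of it, or blinding of staff to it. The aims in Protocol Section 3.1 and in the final SAP do not mention the messaging comparison, and the final SAP gives it no denominator or method.

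**The concern.** Date parity is a quasi-random rule that anyone with a calendar can predict. Staff can know which version applies before eligibility is settled and before the patient is approached, and the outcome of the comparison (agreeing to take part) comes out of that approach. If staff find one framing harder to work with, they might approach fewer doubtful patients on its days, read borderline eligibility differently, or put in less effort.

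The most natural analysis, because it uses the field the form records, is participation by version shown among the patients approached. A difference found that way could come from who was approached and not from how the outcomes were phrased. At stake is an ancillary finding about consent wording.

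**Working it through.** **No plan figure to reproduce.** The documents give no sample size, power, significance level or participation rate for this comparison. The check is therefore of the text, with an illustration.

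**Step 1: is the imbalance in days a problem?** In a 365-day year, seven months have 31 days (16 odd, 15 even), four have 30 (15 and 15) and February has 28 (14 and 14).
- Odd: 7×16 + 4×15 + 14 = 186 (51.0%).
- Even: 7×15 + 4×15 + 14 = 179 (49.0%).

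This is trivial. The weakness is predictability, not unequal numbers.

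**Step 2: where could knowing the version act?**
- *Eligibility:* confirmed by the coordinator with a medical team representative, after the day's version is knowable.
- *Approach:* required for every eligible patient, but Section 4.1 provides for patients who were not approached, so gaps are expected.
- *Receipt:* Section 11.3 expects some patients to see neither version.
- *Effort:* no record of it is described.

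The monthly census checks completeness of screening, not of approach.

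**Step 3: illustration of selective approach.** Assumptions, none from the documents except 1,552 (Protocol Section 8.5), which is used only for scale:
- no true framing effect;
- 30% of eligible patients would accept, so about 1,552 / 0.30 = 5,173 eligible, or about 2,587 per version;
- on one version's days a share s of eligible patients, all would-be refusers, is not approached;
- the denominator is approached patients.

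Apparent acceptance on those days is 0.30 / (1 − s), against 0.30 on the others:

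| s | Apparent acceptance | False difference |
|---|---|---|
| 2% | 0.30 / 0.98 = 30.6% | +0.6 points |
| 5% | 0.30 / 0.95 = 31.6% | +1.6 points |
| 10% | 0.30 / 0.90 = 33.3% | +3.3 points |

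At s = 10%, an assumed acceptance of 20% gives 0.20 / 0.90 = 22.2% (+2.2 points), and 50% gives 0.50 / 0.90 = 55.6% (+5.6 points). If the skipped patients had a 5% chance of accepting instead of none, the 30% case becomes (0.30 − 0.10×0.05) / 0.90 = 32.8% (+2.8 points).

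**Step 4: the same scenario with all eligible patients as denominator, by presentation date.** With only would-be refusers skipped, acceptances on the affected days are unchanged: 0.30×2,587 = 776 of 2,587, which is 30%. The false difference is zero. If the skipped 10% had a 5% chance of accepting, the affected days give 0.30 − 0.10×0.05 = 29.5%, a residual of −0.5 points in place of +2.8.

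**Step 5: what Step 4 does not reach.** If borderline patients are called ineligible more often on one version's days, they leave the eligible denominator and the arithmetic of Step 3 returns. If staff work harder with one version, acceptance itself changes and no choice of denominator corrects it.

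**The case against.** The strongest reply is that the protocol gives staff no discretion over approach, since all eligible patients are to be approached, and that it collects a form on those who are missed. Presentation day is outside staff control. A reader might infer that the recorded data cannot separate framing from selective approach because the form logs the version shown. The documents do not support that: the rule fixes the version from the presentation date, and Step 4 shows that the denominator bias can then be removed. This part of the reply stands. It assumes that presentation date can be recovered for every screened patient, which the rule itself presupposes.

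A reader might also see a design ambiguity in patients who arrive before midnight and are approached after it. There is none. The rule is tied to the day of presentation, and showing the other version would be non-compliance.

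A declined video is also provided for, because the pamphlet carries the same content and comes in both versions.

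The objection does not remove the rest. A requirement to approach everyone does not guarantee that everyone is approached, no analysis by presentation date is specified, and eligibility judgement and effort remain open to influence. That staff know the version is an inference from the date and the lack of any described concealment; the protocol does not say so, nor does it say which version is the positive one.

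**Conclusion.** The point holds as a minor design weakness. Allocation of the messaging version is predictable and unconcealed, and a comparison by version shown among approached patients could be biased. The documents do not show that selective approach happened.

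The size is unknown. The 1.6 and 3.3 points are illustrations at an assumed 30% acceptance with 5% or 10% of eligible patients, all would-be refusers, skipped on one version's days. They also need an approached-only denominator, which the documents do not specify. They should not be read as estimates, and false-positive rates derived from them would rest on the same assumptions.

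A reader might infer that the main trial is compromised. It is not: under Section 4.4.1 treatment is assigned by computer after consent, so the EQ-5D comparison is untouched. The messaging question is not among the trial aims.

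**What to change.** **For patients still to be screened:** replace the odd/even rule with a concealed computer-generated 1:1 list by site. Reveal the version only after eligibility and the decision to approach have been recorded. The data coordinating centre already generates site lists for treatment (Section 8.1).

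**For patients already screened:** state in the SAP that participation will be analysed by the version implied by presentation date, not by version shown, among all eligible screened patients, including those not approached and those who saw neither version. Report eligibility and approach rates on odd and even days, so that version-dependent judgement can be seen even though this analysis does not remove it. Describe the result as quasi-randomised and exploratory.

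**Cost:** one extra list, one extra field on the screening form, and both versions kept available every day. The retrospective part needs analysis only. Effort after the version is revealed stays unblinded under either approach and should be stated as a limitation.
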